DURATION OF SUBJECT PARTICIPATION AND DURATION OF STUDY	
Subjects will be on study for up to 30 days
 
Total Study period: 12 months
 
Enrollment & Follow-up: 1 month
 
The total duration of the study is expected to 12 months. Once enrolled, the test subject will be on the study for one month including recruitment and final subject follow-up.

STUDY METHOD	
The study is based on two visits (VISIT 1 and VISIT 2)
 
 • DAY 0 (enrollment): Subject is queried for inclusion/exclusion criteria and informed about the study. If he/she agrees to participate, inclusion/exclusion criteria and informed consent will be documented. An imaging stent, which bears radiopaque markers, will be also created for each patient. • VISIT 1: Inclusion/exclusion criteria will be reconfirmed and the DE-CBCT imaging will be completed. • VISIT 2 (no more than 30 days since the enrollment): Inclusion/exclusion criteria will be reconfirmed and MDCT imaging completed. 
- Depending on availability of scheduling on MDCT unit, Visit 2 may occur on the same day as Visit 1.

Clinical Assessments	
The following assessments will be performed and recorded on Case Report Form:
 
 • Demographics • Any relevant medical history • Site-specific BD assessment (Region of Interest, ROI) • Adverse Events
PRIMARY ENDPOINT	Jaw BD (HU values) assessed by DE-CBCT and by MDCT
SECONDARY ENDPOINT	Agreement between the BD assessments by evaluators

SAFETY EVALUATIONS	Incidence of adverse events (AE): Adverse events on the days of the study visits will be documented. The PI/staff evaluates the severity of AE and the causal relationship using 'safety evaluation criteria.' The PI will report the case to the investigator/sponsor and IRB subsequently.
PLANNED INTERIM ANALYSES	None
STATISTICS Primary Analysis Plan	
 The correlation between DE-CBCT and MDCT HU values of bone density will be performed using Pearson. The agreement between DE-CBCT and MDCT HU values of bone density will be performed using Bland-Altman plots. In order to evaluate the observer reliability, Kappa statistics will be performed.

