4 STUDY DESIGN

4.1 Overall design

This study will test the hypotheses that DE-CBCT will be equivalent to MDCT to assess BD in the jaw bones.

The study design is an open-label clinical trial to evaluate the effectiveness and accuracy of DE-CBCT to assess BD in jaw bones. This single center trial will enroll 24 subjects, with equal gender distribution. In order to investigate the HU values of bone density across the intended patient population age range, the patients will be recruited according to the three classified age groups. Each study subject will receive both the investigational DE-CBCT and the standard of care MDCT scan, which serves as the control.

Age Group	Number of Patients
Below age 45 (≤ 45 years old)	Male : 4 Female: 4
Older than 45 and less than 65 (45 – 65 years old)	Male : 4 Female: 4
Over age 65 (≥ 65 years old)	Male : 4 Female: 4

The study-specific procedures will be completed in two visits at the UCLA Dental Center and the UCLA Ronald Reagan Hospital. Subjects recruited into the study are those requiring CT imaging for dental diagnosis or treatment planning, including but not limited to implant treatment planning, jaw bone pathoses, impacted teeth etc. In order to mark the ROI area, the dental surgeon will fabricate a custom acrylic stent worn by the patient during imaging. The stent incorporates radiopaque markers that indicate the location(s) and angulation(s) of the proposed ROI area.

The study-specific procedures are as below:

Screening	Informed consent	Study-specific process, 20-30 min
Visit 1	DE-CBCT (experimental scan)	~20 min

Visit 2	MDCT (Standard of care scan)	~20 min
---------	------------------------------	---------

Following scan acquisition, the study's investigators will evaluate the CT scan and make BD assessments at specific locations, as directed by the radiopaque markers in the stent. BD will be assessed in at least three individual sites per subject.

4.2 *Scientific rationale*

The basic premise of this study is that the investigational device (DE-CBCT) will provide accurate estimates of BD in the dento-alveolar bone. The accuracy of DE-CBCT assessments will be determined against the clinical gold standard for BD assessment. The outcome of this study will demonstrate the efficacy and accuracy of DE-CBCT to assess BD at jaw sites.

4.3 *Blinding*

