Evaluators are able to distinguish DE-CBCT and MDCT by appearance and thus cannot be blinded to the modality. However, investigators measuring the BMD will be blinded to the measurements on the standard/experimental CT, and to measurements made by other investigators, until the measurement phase is completed. The statistician will remain blinded, until the data is locked and delivered for statistical analysis.

4.4 *Justification for dose*

Not applicable

4.5 *End of study definition*

A participant will be considered to have completed the study if he/she has completed both scheduled visits including the DE-CBCT and MDCT imaging.

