8.2 Efficacy assessments

BD Assessment

In each patient's MDCT and DE-CBCT scans, discrete regions of interest (ROIs) will be made in the area where radiographic imaging is necessary for the dental diagnosis and treatment plan. The ROI will be angulated, sized, and positioned to mark the treatment area. Using the software tools, the BD will be assessed and recorded. The assessments at each location will be recorded and the HU values of DE-CBCT will be correlated with those of MDCT.

Assessments will be made independently by two oral and maxillofacial radiologists. Each radiologist will make these assessments twice, with at least one month between the two assessments.

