9 STATISTICAL CONSIDERATIONS

In this study, we seek to recruit 24 patients to evaluate the effectiveness and safety of DE-CBCT for assessing jaw bone density compared to the current clinical gold standard for BD measurement, MDCT. This primary objective will be analyzed by correlating DE-CBCT HU values to MDCT HU values and Pearson will be performed for the correlation. The higher the correlation coefficient, the more DE-CBCT correlated to MDCT, meaning DE-CBCT is equivalent to the clinical use of MDCT.

To evaluate the accuracy of DE-CBCT and its equivalence to MDCT, we will analyze the agreement between the two methods using Bland-Altman plots.

To evaluate the intra- and inter-observer reliability, observer we will use Kappa statistics to:

1. Quantify the level of agreement between duplicate assessments by the same radiologist
2. Quantify the level of agreement between independent assessments by the two radiologists

Evaluation analysis group

In this clinical trial, the data from PP analysis group (Per-Protocol Analysis Set) will be analyzed.

① Per Protocol Analysis Set:

The PP analysis group includes subjects who complete the study according to the study plan without a significant violation of the protocol- from voluntarily agreeing to participate in the study to finishing the scanning of both DE-CBCT and MDCT. If the quality of image is affected by the metal prosthesis, the subject corresponding to the image is excluded from the PP analysis group.

② A major violation of the study plan to be excluded from the PP analysis group:

The quality of the image, especially the area where ROI is located, is degraded by the metal prosthesis.

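### Section 9 reads a higher Pearson correlation as equivalence to MDCT, which correlation cannot show; the planned Bland-Altman analysis has no margin or precedence rule, and the powered hypothesis is not equivalence

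*Combined protocol and SAP*

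**What the plan says.** Section 4.1 sets the aim: "This study will test the hypotheses that DE-CBCT will be equivalent to MDCT to assess BD in the jaw bones".

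Section 9 analyses the primary objective by Pearson correlation of the HU values and gives the reading of the result: "The higher the correlation coefficient, the more DE-CBCT correlated to MDCT, meaning DE-CBCT is equivalent to the clinical use of MDCT". Its next paragraph adds: "To evaluate the accuracy of DE-CBCT and its equivalence to MDCT, we will analyze the agreement between the two methods using Bland-Altman plots". The synopsis (section 1.1) lists Pearson, Bland-Altman and Kappa together under the Primary Analysis Plan, with the line "The agreement between DE-CBCT and MDCT HU values of bone density will be performed using Bland-Altman plots".

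The only formal hypothesis is in section 5.1: a null of rho = 0 against rho = 0.89, with two-sided alpha of 0.05 and 80% power. It gives 7 patients, multiplied by three age groups to 21, and raised to 24 for 10% dropout.

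On the data available per subject, section 4.1 says "BD will be assessed in at least three individual sites per subject". Section 8.2 says "Assessments will be made independently by two oral and maxillofacial radiologists" and "Each radiologist will make these assessments twice, with at least one month between the two assessments". Section 9 uses the repeat readings for Kappa, but does not say how readings or sites enter the comparison of the two modalities.

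**The concern.** Correlation measures how closely two sets of values follow a straight line. Equivalence of two HU measurements concerns how far apart they are. A device can track MDCT perfectly in the first sense and be wrong by a fixed amount, or by a fixed proportion, in the second. The sentence in section 9 treats the two as the same.

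The planned Bland-Altman plots address the right question, but the plan gives them nothing to decide with: no acceptable bias, no acceptable limits, no minimum r, and no rule for the case where r is high and the bias is large. In that case the written rule for the primary objective would still allow the result to be reported as equivalence. The stated power gives no protection, because it belongs to a test of association.

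**Working it through.** **1. The plan's own figure.** Inputs from section 5.1: z values 1.960 and 0.842, r0 = 0.89, C(r0) = ½ ln(1.89/0.11) = 1.422.

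n = ((1.960 + 0.842)/1.422)² + 3 = 6.88, rounded up to 7. Then 7 × 3 = 21. For dropout, 21 × 1.1 = 23.1 and 21/0.9 = 23.3; both round up to 24. The plan's numbers reproduce.

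**2. What that power covers.** Power to reject rho = 0 when the true rho is 0.89 is Φ(1.422 × √(n − 3) − 1.96).
- n = 7 (one age group): Φ(2.844 − 1.96) = 81%.
- n = 21 (pooled): Φ(6.03 − 1.96), above 99.9%.

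The smallest r that rejects rho = 0 is t/√(t² + n − 2): about 0.43 at n = 21 and 0.40 at n = 24, with one value per subject. Few readers would call r = 0.43 equivalence.

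**3. Why r cannot show equivalence.** For any constants a and b > 0, the correlation of X with a + bX is 1.
- DE-CBCT = MDCT + 200 HU: r = 1.00, with an error of 200 HU everywhere.
- DE-CBCT = 0.7 × MDCT: r = 1.00, with an error of −105 HU at 350 HU and −375 HU at 1250 HU.

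For scale only, the D4 class in the section 2.2 table runs from 150 to 350 HU, a width of 200 HU. That table is background, not an endpoint.

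**4. What r = 0.89 would imply without any bias.** The documents give no SD of HU values, so 200, 300 and 400 HU are assumed, equal in both modalities. SD of the differences = SD × √(2(1 − 0.89)).

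| Assumed SD (HU) | SD of differences (HU) | 95% limits of agreement, zero bias (HU) |
|---|---|---|
| 200 | 93.8 | ±184 |
| 300 | 140.7 | ±276 |
| 400 | 187.6 | ±368 |

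At SD 300, adding an offset of 200 HU leaves r at 0.89 and moves the limits to 200 ± 276, that is −76 to +476 HU.

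**5. Precision the trial can offer.** One value per subject, 95% CI half-width in SDs of the differences: for each limit, t√(1/n + 1.96²/(2(n − 1))); for the mean bias, t/√n.

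| n | t | Each limit | Mean bias |
|---|---|---|---|
| 21 | 2.086 | 0.79 | 0.46 |
| 24 | 2.069 | 0.73 | 0.42 |

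**6. Feasibility if equivalence is to be claimed.** Simulated at n = 21, zero true bias, r = 0.89, one value per subject. The margins are illustrations, not proposals.

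| Rule | SD 200 | SD 300 | SD 400 |
|---|---|---|---|
| 95% CI of mean bias within ±100 HU | 99% | 74% | 30% |
| 90% CI of mean bias within ±100 HU | over 99% | 87% | 52% |
| 95% CIs of both limits within ±200 HU | 4% | 0.01% | 0% |

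The 90% CI corresponds to two one-sided 5% tests; the 95% CI is stricter.

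**The case against.** The strongest reply is that the plan already contains the right analysis. Section 9 assigns accuracy and equivalence to Bland-Altman plots, and the synopsis puts them in the Primary Analysis Plan. That stands: a large bias would be displayed, and a reader who inferred that the plan has no agreement analysis would be mistaken. But displaying a bias does not decide whether it is acceptable, and the sentence about correlation remains the only stated reading of the result for the primary objective.

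Two safeguards also count for something. The DE-CBCT unit is calibrated on a hydroxyapatite phantom, and a calibration phantom is scanned with the MDCT (section 8.1), which may make a large offset less likely. Section 4.3 says "The statistician will remain blinded, until the data is locked and delivered for statistical analysis", which limits choosing a margin to suit the data. Neither turns r into a measure of agreement, and neither supplies a margin.

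A reader might also infer that the sample size is miscalculated. It is not: the arithmetic reproduces for the hypothesis it tests, and N = 24 is not disputed here. Nor do the documents support inferring that DE-CBCT is biased. The 200 HU offset and the SDs are assumptions, and the 0.89 comes from conventional CBCT against MDCT, not from this device.

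Finally, the handling of readers and sites is not part of the error in the quoted sentence. It matters because no CI for bias or limits can be specified until the unit of analysis is fixed.

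**Conclusion.** The point holds, and the sentence must be changed. A higher r does not mean equivalence, whatever the SDs or the true bias; this follows from the definition of r and needs none of the HU illustrations. Sections 4.1 and 5.1 do not match: the first states an equivalence hypothesis, the second powers a test of rho = 0. No section supplies a margin, acceptable limits or a precedence rule to connect them.

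On size, 21 evaluable subjects with one value each would give a mean bias known to within about ±0.46 SD of the differences and each limit to within about ±0.79 SD. A margin on the mean bias may be within reach at this sample size. A limits rule of ±200 HU would not be, unless agreement is better than r = 0.89 implies. Passing a mean-bias rule would not by itself show that individual readings agree. These feasibility statements rest on the assumed SDs, equal variances, zero true bias and r = 0.89.

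**What to change.** **Section 9.** Delete the sentence equating correlation with equivalence and report Pearson's r as supportive only. Base the conclusion on the Bland-Altman mean bias and 95% limits of agreement, each with a 95% CI. Use one pre-specified value per subject, or a model with subject as a random effect for the three or more sites. State how the two radiologists' two readings are combined; if they are averaged, say that the limits apply to that average and not to a single reading.

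**Section 1.1.** Make the matching edits to the Pearson and Bland-Altman lines.

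**Sections 4.1 and 9, sponsor's choice.** Either remove the words equivalent and equivalence, or, if equivalence is to be claimed, fix a clinically justified HU margin before any readings are made. In the second case, state the CI level (90% for two one-sided 5% tests, 95% being stricter) and whether the rule applies to the mean bias, the limits or both.

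**Section 5.1.** Keep N = 24. Say that the 80% is the power to reject rho = 0 when the true rho is 0.89, at n = 7 in one age group (above 99.9% pooled at n = 21), and that this test shows association and not equivalence. Add the precision for the chosen unit: with one value per subject, 0.79 SD per limit and 0.46 SD for the mean bias at n = 21 (0.73 and 0.42 at n = 24).

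**Cost.** A modest change of analysis and edits to four sections, with no new patients or scans. Without a margin, the equivalence claim is given up; with one, the chance of success depends on the rule chosen, as the working shows.

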3.2 Secondary objective

To analyze the agreement between the BD assessments by the evaluators

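### Kappa is the only statistic planned for reader agreement on numeric HU readings, with no categories, cut points or weights defined (secondary endpoint)

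*Combined protocol and SAP*

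**What the plan says.** The primary endpoint in the synopsis (section 1.1) is "Jaw BD (HU values) assessed by DE-CBCT and by MDCT". The secondary endpoint is "Agreement between the BD assessments by evaluators", and section 3.2 gives the matching and only secondary objective: "To analyze the agreement between the BD assessments by the evaluators".

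Under section 8.2, two radiologists work independently. Each measures bone density in every region of interest with software tools, and each repeats the measurement at least one month later. The section continues: "The assessments at each location will be recorded and the HU values of DE-CBCT will be correlated with those of MDCT". Section 4.1 requires at least three sites per subject.

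The synopsis statistics row says "In order to evaluate the observer reliability, Kappa statistics will be performed". Section 9 says "To evaluate the intra- and inter-observer reliability, observer we will use Kappa statistics to" serve two purposes, the first being "Quantify the level of agreement between duplicate assessments by the same radiologist" and the second the same comparison between the two radiologists. Neither place gives categories, cut points, weights, a Kappa variant or a confidence interval.

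Agreement on the HU scale is planned only between devices: "we will analyze the agreement between the two methods using Bland-Altman plots".

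**The concern.** Kappa corrects the proportion of identical (or, with weights, nearly identical) classifications for chance, so it needs classes. The plan records HU as numbers and analyses them as numbers everywhere else (Pearson, Bland-Altman). To compute Kappa, someone must group the HU values and decide on weights, and nothing stops that from happening after the readings have been seen.

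Two things follow. First, the plan does not determine the one secondary result, because the same readings can look poor or excellent depending on the grouping. Second, Kappa is not expressed in HU. The trial asks whether two devices give equivalent HU values, and a reader of the device differences would want to know how much of that spread comes from the radiologists. Kappa does not tell them.

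**Working it through.** **Is there a category definition anywhere?** The only HU classes are the D1–D4 bands in the background table of section 2.2, with cuts at 150, 350, 850 and 1250 HU. The synopsis statistics row and sections 8.2 and 9 do not refer to them. Section 2.2 itself describes the scheme as subjective. The bands share end points at 350 and 850, have no class below 150 HU and carry no weights. They cannot be taken as the planned categories.

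**Is there a stated figure to reproduce?** None for Kappa: no expected value, precision or threshold is given. The sample size in section 5.1 concerns the primary correlation and does reproduce: ((1.960 + 0.842)/1.422)² + 3 = 6.88, rounded up to 7; 7 × 3 = 21; 21 × 1.1 = 23.1, rounded up to 24.

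**How much does the unstated choice matter?** The documents give no HU mean, SD or reader error, so these inputs are assumptions.

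- Sites: 21 subjects × 3 = 63.
- True HU: normal, mean 700, between-site SD 300.
- Two readings per site, each with independent normal error of SD s, rounded to whole HU.
- 2,000 simulated data sets per setting; the mean Kappa is shown.
- ICC = 300²/(300² + s²). For s = 50: 90,000/92,500 = 0.97.

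| Statistic | s = 10 | s = 30 | s = 50 | s = 100 |
|---|---|---|---|---|
| ICC | 0.999 | 0.99 | 0.97 | 0.90 |
| Kappa, 50-HU bins | 0.76 | 0.39 | 0.23 | 0.10 |
| Kappa, 100-HU bins | 0.87 | 0.63 | 0.43 | 0.20 |
| Kappa, 200-HU bins | 0.93 | 0.79 | 0.65 | 0.37 |
| Kappa, section 2.2 cuts plus a class below 150, unweighted | 0.96 | 0.86 | 0.77 | 0.57 |
| Same cuts, quadratic weights | 0.98 | 0.93 | 0.89 | 0.78 |
| Section 2.2 cuts, below 150 merged into D4, unweighted | 0.96 | 0.88 | 0.80 | 0.61 |

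The equal-width bins are ours and only show that the choice is open. With mean 600 and SD 200 the pattern is the same: at s = 50 the ICC is 0.94, and Kappa is 0.40 (100-HU bins), 0.69 (section 2.2 cuts with a class below 150, unweighted) or 0.77 (same cuts, quadratic). A within-subject correlation of true HU of 0.5, or 72 sites instead of 63, moves these values by at most 0.02.

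**Does Kappa identify reader error in HU?** Solving for the s that gives unweighted Kappa = 0.80 on the section 2.2 cuts with a class below 150, and converting to inter-reader 95% limits with 1.96 × √2 × s = 2.772 × s:

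| Assumed mean, SD (HU) | s (HU) | Limits of agreement (HU) | ICC = SD²/(SD² + s²) |
|---|---|---|---|
| 500, 200 | 31.0 | ±85.9 | 0.977 |
| 600, 200 | 31.6 | ±87.6 | 0.976 |
| 700, 300 | 43.2 | ±119.7 | 0.980 |
| 900, 400 | 54.5 | ±151.1 | 0.982 |

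One Kappa value covers reader errors that differ by a factor of 54.5/31.0 = 1.76.

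**The case against.** The secondary endpoint and the Kappa sentence speak of assessments, not HU, and section 2.2 discusses bone density in classes. The authors may have meant readers to agree on a class, where Kappa would be legitimate. But no section says so, and section 8.2 describes a software measurement with HU values recorded. Even on that reading, the classes and weights remain undefined.

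Three further points stand in part.

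- The between-device Bland-Altman limits already contain reader error, so a separate HU-scale reader error is helpful for interpreting them rather than indispensable.
- The ICC also depends on the spread of HU: in the second table it barely moves (0.976 to 0.982) while reader error nearly doubles. An ICC alone would not solve the second problem; the limits of agreement and within-reader SD do.
- How values below 150 HU are handled matters little. It shifts unweighted Kappa by at most 0.04 (0.57 against 0.61), while the sampling SD of that Kappa at 63 sites is about 0.04 to 0.09. The choice of classes and weights matters more: at s = 100, quadratic weights move the same cuts from 0.57 to 0.78.

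Finally, because duplicate readings are planned, HU-scale agreement could still be computed afterwards. It would then not be prespecified.

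**Conclusion.** The concern holds and should be fixed. The sole analysis of the only secondary objective applies a categorical statistic to numeric readings, and its value rests on a choice the plan does not make. Under the assumed mean 700, SD 300 and reader error SD 50 HU, that choice moves Kappa between 0.23 and 0.89. If only the section 2.2 cuts with a class below 150 are allowed, unweighted or with quadratic weights, the range is 0.77 to 0.89. These figures show sensitivity and do not predict the trial's result, since every HU input is assumed. That the plan leaves Kappa undefined and plans no reader agreement in HU rests on the text alone.

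The reach is limited: the primary Pearson and Bland-Altman analyses, the sample size and any decision threshold are untouched.

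**What to change.** In sections 1.1 and 9, replace the Kappa sentences with text along these lines:

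- Reader agreement on HU is analysed separately for DE-CBCT and MDCT.
- Between radiologists: absolute-agreement ICC, with the model stated in advance and a 95% CI, plus the mean inter-reader difference and 95% limits of agreement in HU.
- Within radiologist: within-reader SD or repeatability coefficient in HU, plus ICC, from the duplicate readings.
- Intervals allow for several sites per subject.
- State which of each radiologist's two readings enters the between-reader comparison.

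Kappa can stay as a supplement if the HU classes (including values below 150 and at the shared end points) and the weights are fixed before the readings are made. Defining them alone would remove the ambiguity but would still give no reader error in HU.

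The cost is revised wording and a little more analysis. Sections 4.3 and 8.2 already provide two independent radiologists, duplicate readings and blinding to each other's measurements, so no new data are needed.

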5.3 Exclusion criteria

- Pregnancy
- Patients who are unable to comprehend the risks of the study to provide informed consent
- Extensive dental restorations, maxillofacial prosthesis, or orthopedic hardware that likely may cause artifacts and degrade quality, as determined by the study radiologists.

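### The only analysis set drops subjects after scanning for metal-degraded images, without separating DE-CBCT from MDCT or requiring the call before HU values are known

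*Combined protocol and SAP*

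**What the plan says.** Section 9 (Evaluation analysis group) names one analysis population: "In this clinical trial, the data from PP analysis group (Per-Protocol Analysis Set) will be analyzed". No all-scanned set and no sensitivity set is defined. Membership runs from consent "to finishing the scanning of both DE-CBCT and MDCT", with one image-based exclusion: "If the quality of image is affected by the metal prosthesis, the subject corresponding to the image is excluded from the PP analysis group". The same section gives the only listed major violation as "The quality of the image, especially the area where ROI is located, is degraded by the metal prosthesis".

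Metal is also screened for before scanning. Section 5.3 excludes extensive restorations, prostheses or hardware "that likely may cause artifacts and degrade quality, as determined by the study radiologists".

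On blinding, Section 4.3 says "Evaluators are able to distinguish DE-CBCT and MDCT by appearance and thus cannot be blinded to the modality". It adds a protection, which ends when measurement is finished: "investigators measuring the BMD will be blinded to the measurements on the standard/experimental CT, and to measurements made by other investigators, until the measurement phase". Until the data are locked, the statistician is blinded as well. Section 4.3 does not mention the image-quality exclusion.

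**The concern.** The Section 9 rule is a second, subjective filter that follows the Section 5.3 screen and can be applied only after the scans exist. Two things follow.

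First, the rule treats all images alike. When metal spoils the DE-CBCT but not the MDCT, the test device has given no usable value at a site where the reference did. That bears on the device, yet the subject is deleted in the same way as one whose reference scan was spoiled. This happens when the rule is followed exactly, and it needs no bad faith.

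Second, no timing is attached to the call. If it can be made when both sets of HU values are known, the exclusion can depend on the observed difference, and agreement then looks better than it is. Section 9 reads a higher correlation as equivalence and sets no threshold for r or limit for the differences, so any upward shift feeds directly into the claim.

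**Working it through.** **The plan's own figure.** Section 5.1 uses n = ((z for alpha/2 + z for beta) / C(r0))² + 3 with C(0.89) = 1.422. This gives (2.802 / 1.422)² + 3 = 6.88, rounded up to 7. Then 7 × 3 = 21, and 21 × 1.1 = 23.1, rounded up to 24. The figure reproduces. Power against a correlation of zero is not the issue here: at r = 0.89 it stays above 0.999 with 18 to 24 subjects.

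**What the rule does in each case.**

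| DE-CBCT | MDCT | Section 9 result | What the case tells us |
|---|---|---|---|
| degraded by metal | readable | subject dropped | test device not evaluable where the reference was |
| readable | degraded by metal | subject dropped | reference not evaluable |
| degraded by metal | degraded by metal | subject dropped | site not assessable by either |

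The three cases cannot be told apart in the result, because Section 9 does not ask for the modality.

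**When the call could be made.**
- Before measurement: no HU values exist, so there is no selection on disagreement.
- During measurement: Section 4.3 keeps readers from the other modality's values, so they cannot select on disagreement.
- After measurement and before lock: the readers' blinding has ended, and nothing prevents the call being made here.

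**How much selection could matter.** No document gives the number of metal-bearing subjects or the error SD, so these are assumptions: 24 subjects, one HU pair each, bivariate normal values with equal SDs and no mean bias, 40,000 simulated sets. Dropped subjects are those with the largest absolute difference among those who can be dropped. The width of the Bland-Altman limits is 2 × 1.96 × SD of the differences, so the width ratio equals the SD ratio. True r is 0.80; with nobody dropped, median r is 0.81.

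| Who can be dropped | Dropped | SD ratio | Limits narrower by | Median r |
|---|---|---|---|---|
| any of 24 | 2 worst | 0.83 | 17% | 0.86 |
| any of 24 | 3 worst | 0.77 | 23% | 0.88 |
| 5 metal-bearing, ordinary errors | 2 worst | 0.95 | 5% | 0.82 |
| 4 metal-bearing, ordinary errors | 2 worst | 0.96 | 4% | 0.82 |
| 3 metal-bearing, ordinary errors | 2 worst | 0.98 | 2% | 0.81 |

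At a true r of 0.89, dropping the 2 worst of any 24 moves median r from 0.89 to 0.93. Dropping subjects at random leaves r essentially unchanged, so the effect comes from selection and not from the smaller number.

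If metal inflates the differences, the effect grows. For example, if 2 of 24 DE-CBCT scans had three times the usual error SD, including them would widen the limits by a factor of √((22 × 1 + 2 × 9) / 24) = √(40 / 24) = 1.29. Both the 2 scans and the factor 3 are invented for illustration.

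**The case against.** The strongest reply has four parts.

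1. **Blinding.** A reader might infer that the exclusion is made with the HU values in view. The documents do not say so; they are silent on this decision. Section 4.3 also blocks the obvious route, because choosing subjects by disagreement needs both values, readers lack the other modality's values during measurement, and the statistician is blinded until lock. This stands. What remains is the interval between the end of measurement and lock, and any person whom Section 4.3 does not cover.

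2. **Scope.** A reader might also infer that any poorly agreeing subject, or any failed DE-CBCT, can be removed under this clause. It cannot. The clause covers degradation by a metal prosthesis only, and poor images from motion, noise or scatter stay in. This also stands.

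3. **Rationale.** Section 5.3 already places extensive metal outside the intended population, so Section 9 may only be catching what screening missed. That is a fair reason to have the rule. But Section 5.3 is limited to extensive work judged likely to cause artefact, while Section 9 removes any subject whose image is affected, including some who were properly enrolled. It is not a reason to leave DE-CBCT-only cases uncounted.

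4. **Magnitude.** Dropping the worst 2 or 3 of all 24 does not model a rule confined to metal-bearing subjects. This stands, and the smaller figures in the table are closer to the rule as written if metal leaves the errors ordinary. Section 4.1 also plans at least three sites per subject, so none of the percentages transfers directly to the planned data.

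**Conclusion.** The concern holds in a limited form. The sole analysis set excludes whole subjects after scanning for metal-degraded images. It does not separate the two modalities, and nothing requires the decision to precede knowledge of the HU values. DE-CBCT scans spoiled by metal while the MDCT was readable therefore leave the accuracy result with no requirement to report them. That part would stand even with perfect blinding.

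The documents do not show that the exclusion will be made unblinded or that selection would occur. The part about timing is a missing safeguard.

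With one normal pair per subject, the effect on the limits runs from about 2 to 5% (3 to 5 metal-bearing subjects with ordinary errors) to about 17% (the 2 worst of any 24 dropped). The second is an upper bound for two exclusions with ordinary errors, not an expectation. If metal inflates the differences, the effect exceeds the 2 to 5% range by an amount the documents do not allow one to estimate. The change should be made before measurement starts, because it cannot be repaired credibly once the values are known.

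**What to change.** In Section 9:

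- Have the study radiologists make the metal-artefact call separately for each scan, against a criterion written in advance, and lock it before any HU value is measured.
- Record which modality was affected, and report the number of subjects whose DE-CBCT alone was non-evaluable.
- Keep the per-protocol analysis, and repeat the Pearson and Bland-Altman analyses as a sensitivity analysis in all subjects who have both scans and measurable ROIs.

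The cost is a paragraph of text, one CRF field per scan and one repeat analysis. It uses the existing readers and needs no further subjects or scans. The downside is that the reported limits may be wider.
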